1.1 Data Management and Data Quality

The first randomization involves allocation to CPS vs. SMS using a 1:1 allocation ratio. This step will use stratified randomization in permuted blocks to achieve balance in distribution of behaviorally and perinatally infected youth. The REC data team will program the randomizer in Qualtrics and will not participate either in the intervention delivery or in the adherence reinforcement steps. The protocol team will monitor race, ethnicity, and gender to ensure balanced distribution at the first stage. After 6 months, stratified randomization will occur with permuted blocks within each trajectory. Since second stage randomization is dependent on first stage response status, we will only maintain the balance within each first stage treatment outcome when randomizing at the second stage.

Following the Analytic Core's (AC) standard quality assurance, including checking for outliers and abnormal values using graphical methods, we will verify that the distributions of measures meet the assumptions of the statistical tests to be used, applying a formal test such as the Shapiro-Wilk's test [60]. Transformations will be used when distributional assumptions are not fulfilled. Tests will be conducted to identify potential relationships among baseline demographic and clinical variables and our dependent variables and to see whether they are balanced between groups. If a baseline variable is not balanced between groups and is correlated with the dependent variable ($r > .30$), we will include this variable as a covariate in subsequent analyses. Since we will test more than one primary hypothesis with one primary outcome variable (VL suppression), the Hochberg step-up multiplicity adjustment will be used with a two-tailed family wise alpha-level of .05 [61]. All other tests described below will each have a two-tailed alpha-level of 0.05. Outcome analyses will be based on the principle of intention-to-treat [62].

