1.2.1 Primary Analysis Plan

The primary analysis will be a comparison of SRA (primary outcome) between the CPS and the SMS group at the end of first stage of randomization. This will be performed using a χ^2 test. We will also compare the VL suppression between the two groups for those available subjects, albeit this is no longer treated as primary outcome. Since SRA (and VL) is a continuous measure, we will use two-sample t-test to conduct this analysis. We will also compare the self-reported medication adherence rate (secondary outcome) between the two groups using a χ^2 test. All the primary analyses will be based on initial assignment to groups, using the ITT principle. Each of the primary hypotheses will be tested using linear mixed-effects (LME) regression analyses.¹⁰⁴ For testing primary hypothesis 1 (PH1), the model will include up to 3 repeated assessments of VL suppression (weeks 0/baseline, 12, 24, 36, 48). For primary hypothesis 2 (PH2), we will only focus on non-responders (for both CPS and SMS at stage 1) and compare the SRA as dependent variable using a repeated measure LME (weeks 0/baseline, 12, 24, 36, 48). In an effort to get the outcome for PH2 some subject may have final outcome at latter date than 48 weeks. Each LME model will include a random intercept and slope and fixed effects for adherence intervention group, and time, as well as the stratification variables: clinical site, age, gender. A likelihood ratio test will examine the incremental contribution of the group by time interaction, which represents the interaction of interest for PH1 and PH2, testing for a differential adherence intervention effect over time. The decision rule for each primary hypothesis calls for rejection of H_0 if this interaction is statistically significant using the Hochberg adjustment. A site by group interaction will be also examined and included in each model (above) if significant at the 0.05 level. The purpose of the LME based analysis for the primary aim is to determine which of the first-stage intervention, CPS or SMS, is associated with the most improvement in VL and adherence, regardless of which second-stage treatment participants received. Due to contraction of sample size compared to our original plan, we do not plan to adjust α for multiple of testing. In addition to PH1, for those subjects we have VL suppression data available we would perform similar LME to test for its significance. We also expect some subjects with complete VL data and many with partial VL data for

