1.2.4 Sample Size and Power

Sample Size and Power. Statistical power analyses examined the sample size requirements to detect greater than chance group differences on primary outcome (PH1 and Ph2). We have used Susan's formula with a total sample size of 120.

<http://people.seas.harvard.edu/~samurphy/papers/APPProof.pdf>

| Power Table | | | |
|--------------------|------------|------------|-----------------------------|
| ES | p | N | N(10% attrition adjustment) |
| 0.55 | 0.4 | 86 | 96 |
| | 0.5 | 104 | 116 |
| | 0.6 | 130 | 144 |
| | 0.7 | 174 | 192 |
| 0.6 | 0.4 | 74 | 80 |
| | 0.5 | 88 | 98 |
| | 0.6 | 110 | 120 |
| | 0.7 | 146 | 160 |

Alternatively, for the two groups comparison this corresponds to n=60/group. This sample size is sufficient to provide 80% power (or more) for a standardized Effect Size (ES) of 0.55 or more, using a t-distribution for a two tailed test with $\alpha=0.05$, with 10% attrition assuming equal responder rate (p) in both arms.

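### The SAP's 80% power at an effect size of 0.55 belongs to a two-sample t-test and does not cover the chi-square, the yes/no composite or the mixed-model interaction that it also treats as primary

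*SAP*

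**What the plan says.** SAP 1.2.4 is the SAP's only power statement. It takes a total of 120 and says that "for the two groups comparison this corresponds to n=60/group". It then says: "This sample size is sufficient to provide 80% power (or more) for a standardized Effect Size (ES) of 0.55 or more, using a t-distribution". The conditions attached are "for a two tailed test with $\alpha=0.05$, with 10% attrition" and "assuming equal responder rate (p) in both arms".

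SAP 1.2.1 describes the analysis that this power should support, but names three tests:

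- **Chi-square.** "The primary analysis will be a comparison of SRA (primary outcome) between the CPS and the SMS group" at the end of stage 1, and the next sentence assigns a chi-square test to it.
- **Two-sample t-test.** Shortly after, it says that SRA, like viral load, "is a continuous measure, we will use two-sample t-test to conduct this analysis".
- **Linear mixed-effects model.** Each primary hypothesis is then to be tested by this model, and the null is rejected on the group-by-time interaction.

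SAP 1.2 adds a fourth element. If viral suppression and SRA agree in at least 80% of cases, the primary outcome is suppression where available and SRA otherwise. That outcome is binary, and the SAP says it will be sufficiently powered.

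No SRA cut-off is given for use as an outcome (the only one, 80%, is in the protocol's eligibility criteria). No expected CPS and SMS proportions are given, and ES is not defined for a binary outcome.

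**The concern.** A power figure belongs to one test, one outcome scale and one effect. The figure in 1.2.4 is for a difference in means in SD units. A chi-square compares proportions, and cutting a continuous score to yes/no discards information, so a shift detectable with 80% power by a t-test is detected less often after the cut. The mixed-model interaction is a different contrast again, with its own variance.

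What is at stake is how a null result is read. If the chi-square or the composite is reported as primary and is not significant, readers of 1.2.4 will take it that an effect of 0.55 had an 80% chance of detection. The SAP does not establish that for either analysis.

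**Working it through.** **Inputs.** From SAP 1.2.4: 60 per group, 10% attrition, two-sided alpha 0.05, ES 0.55. From SAP 1.1: "The first randomization involves allocation to CPS vs. SMS using a 1:1 allocation ratio". Analysable n = 60 × 0.9 = 54 per arm.

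**1. The plan's own figure.** Noncentral t with 2 × 54 − 2 = 106 degrees of freedom and noncentrality 0.55 × √(54/2) = 2.858. The critical value is 1.983. Power = **80.8%** (84.8% with 60 per arm). The stated figure reproduces.

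**2. Chi-square, with 0.55 read in SD units.** Assume a normal score, an SMS success rate p₁ and a CPS rate p₂ = Φ(Φ⁻¹(p₁) + 0.55). With p̄ the mean of the two rates,

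power = Φ{ [ (p₂ − p₁)√n − 1.96 √(2p̄(1 − p̄)) ] / √(p₁(1 − p₁) + p₂(1 − p₂)) }.

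For p₁ = 0.50: p₂ = 0.709 and p̄ = 0.604. The bracket is 1.535 − 1.355 and the divisor is 0.676, giving Φ(0.265) = 60.5%.

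**3. Chi-square, with 0.55 read as Cohen's h.** Here p₂ = sin²(arcsin√p₁ + 0.275), with the same power formula.

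The SMS rates of 40–70% are an assumption. They match the range of p in the 1.2.4 table, but that p is a responder rate and is not offered as the SMS rate for this test. All rows use 54 per arm.

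| SMS rate | CPS rate, 0.55 SD shift | Power | CPS rate, h = 0.55 | Difference | Power |
|---|---|---|---|---|---|
| 40% | 61.7% | 61.7% | 67.1% | 27 points | 81.5% |
| 50% | 70.9% | 60.5% | 76.1% | 26 points | 81.2% |
| 60% | 78.9% | 57.0% | 84.1% | 24 points | 80.7% |
| 70% | 85.9% | 51.2% | 91.0% | 21 points | 79.5% |

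**4. How far the SD-unit figure moves.** With 60 per arm and no attrition it is 56–66% at the same SMS rates. With a continuity correction at 54 per arm it is 42–53%. A logistic in place of a normal conversion gives 64–72% at SMS rates of 20–60%. At an SMS rate of 80% the normal conversion gives 42%. All of these are below 80%.

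**5. Differences that give exactly 80% with 54 per arm.** 40% against 66.6%, 50% against 75.8%, 60% against 84.0%: about 24–27 points.

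**6. The role of p in the 1.2.4 table.** N × (1 − p) is 86 × 0.6 = 51.6, 104 × 0.5 = 52, 130 × 0.4 = 52 and 174 × 0.3 = 52.2 at ES 0.55, and about 44 in every row at ES 0.6. So p only scales the table's N. It does not enter the two-group calculation in step 1.

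**7. The mixed-model interaction.** The SAP gives no slope difference, within-subject correlation or variance for the current design, so its power cannot be derived from the SAP's inputs.

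**The case against.** The best defence is that the power statement does match a named test: 1.2.1 calls SRA continuous and names a two-sample t-test, and for that test the 80% is right. This stands. The chi-square is neither the only test named nor the one on which the decision rule rests.

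The second defence is that 51–62% is not fixed by the documents. This also stands. The range needs a normal score, a cut at an unstated threshold, SMS rates of 40–70% and 54 per arm. On the Cohen's h reading the shortfall disappears. A reader might infer that the true power of the primary analysis is 51–62%, or that the SAP's arithmetic is wrong; the documents support neither. The SD reading is still the more natural one, because 1.2.4 refers to a t-distribution. And the h reading leaves a gap of its own: the SAP nowhere says that it relies on a difference of 21–27 points.

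A reader might also infer that assuming equal responder rates in both arms undermines the 80%, since the arms are being compared on response. It does not: the two-group figure makes no use of p (step 6).

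Finally, it might seem that making the t-test primary settles everything. It would settle the SRA comparison, if SRA is close enough to normal, but a t-test power figure cannot be carried over to the yes/no composite or to the interaction.

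**Conclusion.** The point holds in this form. The 80% at 0.55 is correct for a two-sample t-test with 54 per arm, and for that test only. It does not cover the chi-square assigned to the primary SRA comparison, the binary composite, or the interaction that decides rejection.

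For the chi-square, power is about 51–62% if 0.55 is an SD shift in a normal score that is then cut (SMS rates 40–70%, 54 per arm), and about 80% if 0.55 is Cohen's h. Which applies cannot be settled from the documents, because ES, the cut-off and the arm rates are undefined.

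All figures use alpha 0.05, following the statement in 1.2.1 that "we do not plan to adjust α for multiple of testing". The decision rule in the same section still cites Hochberg. At alpha 0.025 the t-test itself has 72.0% power with 54 per arm.

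**What to change.** In SAP 1.2.1, name one deciding primary test. In 1.2.4, restate the power for that test.

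- **If the outcome is binary** (dichotomised SRA or the composite): state the SRA cut-off, name the expected CPS and SMS rates, and replace the 80% at ES 0.55 with chi-square power for those rates. As a guide, 80% needs a difference of about 24–27 points at SMS rates of 40–60%, while a 0.55 SD shift gives roughly 50–60%.
- **If continuous SRA by t-test is made primary for SRA**: keep the 80% for that test only, report the chi-square as supportive, and claim no 80% for the composite or the interaction.
- **If the mixed-model interaction remains the deciding test**: give power for it, with the slope difference and correlation assumed.

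State the alpha used alongside the figure, so that it agrees with the decision rule. The equal-responder-rate condition need not change for the two-group figure.

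The cost is wording, plus a less favourable stated power on the binary route unless a difference of about 24–27 points can be justified. The t-test route costs nothing against the figure now stated.

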1.2.5 Strategies for Attrition

Attrition introduces bias and reduces power, precision and generalizability [71]. In keeping with the Intent-to-Treat principle we distinguish between intervention and study termination (complete withdrawal). Accordingly, we will make every effort to continue assessments for the entire course of randomized intervention, even among those who do not continue with randomized group [72]. The mixed-effects models will incorporate all available data, even from subjects who do not complete the study. Mixed-effects models yield valid inferences assuming ignorable attrition [73]. For conducting descriptive and two-group comparison Multiple Imputation will be used to replace missing values in the outcomes and other measures. Point estimates, standard errors, and all tests will be calculated using Rubin's rules for combining the results of identical analyses performed on each of the imputed data sets [74].

1.2.6 Additional Secondary Aims

Self-management model analysis will be conducted based on the exploration, preparation, implementation, sustainment (EPIS) model. For the implementation aim, we will explore provider perceptions of the centralized implementation intervention and of the intervention as an evidence-based

practice, through qualitative interviews and quantitative assessments based on the EPIS model. Data coding and analysis will proceed in a three-phase process with the EPIS Team. First, consistent with Morgan's [75] recommendations for qualitative content analyses and Hsieh and Shannon's [76] directed qualitative content analytic approach, standard definitions of the concepts to be coded in the text will initially be developed by the ISC based on the EPIS model. We will first systematically review each interview at each time point for all thematic mentions of EPIS model constructs, initially using existing theory to guide categorization, but also allowing themes to emerge from the data through open coding procedures [77, 78]. This combined inductive and deductive coding approach will allow us to both validate and extend the EPIS framework through our analysis. Revision of our initial coding categories will occur iteratively until we reach saturation in the identification of new codes. During this iterative process, categories and their definitions will be refined and sub-categories of codes consolidated, consistent with an axial-coding process. At this point, we will return to each interview and systematically apply the final, revised set of codes. In addition, case codes will be applied to each interview to reflect clinic role, site, cluster, and relevant demographic characteristics of the respondent. All coding will be conducted using NVIVO Version 10. For reliability, a random selection of 30% of the interviews will be independently coded. Coding will be monitored to maintain a kappa coefficient of .90 or higher [79, 80]. Any discrepancies will be discussed and resolved. We will work closely with the EPIS team and then ISC to develop an Intervention Profile and Implementation Resources for replication and sustainment of the intervention. The Profile will synthesize intervention components and implementation analyses into intervention-specific practical guidance for further scale up. Additional resources to facilitate uptake, quality implementation, and sustainment of effective interventions are described in the ISC.
